7.3. Source Documentation

Source data is all information, original records of clinical findings, observations, or other activities in a clinical trial necessary for the reconstruction and evaluation of the trial. Source data are contained in source documents. Examples of these original documents, and data records include: hospital records, clinical and office charts, laboratory notes, memoranda, subjects' diaries or evaluation checklists, pharmacy dispensing records, recorded data from automated instruments, copies or transcriptions certified after verification as being accurate and complete, microfiches, microfilm or magnetic media, x-rays, subject files, and records kept at the pharmacy, at the laboratories, and at medico-technical departments involved in the clinical trial.

7.4. Data and Source Documentation

Velos, an electronic database capture system will be created to record the data for this trial. Research coordinators will input clinical trial data into the database. This database is password protected and only the PI, assigned research coordinator, and CTO quality assurance specialists will have access to the database. Velos is the primary data collection instrument for the study. All data requested in Velos must

be reported. All missing data must be explained. The quality assurance specialists will monitor this trial every 6-8 weeks for data entry accuracy.

7.5. Recording of Data and Retention of Documents

All information required by the protocol should be recorded in source documents and CRFs; any omissions or corrections should be explained.

All entries to the CRFs must be clear and must be completed in black ball-point pen to ensure the legibility of self-copying or photocopied pages. Corrections will be made by placing a single horizontal line through the incorrect entry, so that the original entry can still be seen, and placing the revised entry beside it. The revised entry must be initialed and dated by a member of the Investigator's research team authorized to make CRF entries. Correction fluid must not be used.

The Investigator must maintain source documents for each subject in the study. All information on CRFs will be traceable to these source documents, which are generally maintained in the subject's file. The source documents will contain all demographic and medical information (eg, laboratory data, ECGs, diagnostic test results, assessment of presence or absence of adverse events, changes in concomitant medications), and a copy of the signed ICF, which should indicate the study number and title of the study.

Essential documents, as listed below, will be retained by the Investigator for as long as needed to comply with national regulations.

Essential documents include:

1. Signed protocol and all amendments;
2. IRB approvals for the study protocol and all amendments;
3. All source documents and laboratory records;
4. CRF copies;
5. Signed ICF for both screened and enrolled subjects; and
6. Any other pertinent study document.

8. STUDY MONITORING, AUDITING AND INSPECTING

8.1. Study Monitoring Plan

This study will be monitored according to the monitoring plan detailed below. The investigator will allocate adequate time for such monitoring activities. The Investigator will also ensure that the monitor or other compliance or quality assurance reviewer is given access to all the above noted study-related documents and study related facilities (e.g. pharmacy, diagnostic laboratory, etc.), and has adequate space to conduct the monitoring visit. A risk-based, data-driven monitoring approach will be used to verify data for this trial which will also include a centralized review of data for quality, trends, consistency and general safety review. A quality assurance specialist will make regularly scheduled trips to the investigational site to review the progress of the trial, study data and site processes. At each visit, the

monitor will review various aspects of the trial including, but not limited to: screening and enrollment logs; compliance with the protocol and study manual and with the principles of Good Clinical Practice; completion of case report forms; source data verification; study drug accountability and storage; facilities and staff.

During scheduled monitoring visits, the investigator and the investigational site staff must be available to meet with the quality assurance specialist in order to discuss the progress of the trial, make necessary corrections to case report form entries, respond to data clarification requests and respond to any other trial-related inquiries of the monitor. In addition to on-site monitoring visits, the Sponsor-investigator and/or representatives will also be routinely reviewing data. Any queries identified through this review will be managed within the systems established for query resolution and tracking. Inquiries related to study conduct, which require further information or action will be discussed within the study team for appropriate and documented escalation plans. It is expected that response to data clarification requests and other trial-related inquiries will occur throughout the course of the study through regular communication with the site monitor, the Sponsor-investigator or representatives, and review/entry of data into the electronic study database.

At any time during the course of the study, representatives of the FDA and/or local regulatory agencies may review the conduct or results of the study at the investigational site. The investigator must promptly inform Bristol Myers Squibb of any audit requests by health authorities, and will provide BMS with the results of any such audits and with copies of any regulatory documents related to such audits.

The investigator will allocate adequate time for such monitoring activities. The Investigator will also ensure that the monitor or other compliance or quality assurance reviewer is given access to all the above noted study-related documents and study related facilities (e.g. pharmacy, diagnostic laboratory, etc.), and has adequate space to conduct the monitoring visit.

At the NYU Perlmutter Cancer Center, all investigator-initiated protocols are subject to a standardized data and safety monitoring, which includes scientific peer review, IRB review and DSMC review as well as internal auditing.

The review of AEs and trial conduct for this trial occurs at several levels:

- (1) Principal Investigator: Adverse events are evaluated monthly by the principal investigator in conjunction with the research nurses, data manager and research team.
- (2) DSMC, twice annually
- (3) Institutional Review Board (IRB): An annual report to the IRB is submitted by the trial PI for continuation of the protocol. It includes a summary of all AEs, total enrollment with demographics, protocol violations, and current status of subjects as well as available research data.
- (4) In addition, the quality assurance unit will monitor this trial every 6-8 weeks, to verify adherence to the protocol; the completeness, accuracy and consistency of the data; and adherence to ICH Good Clinical Practice guidelines.

8.2. Auditing Procedure

In addition to the routine monitoring procedures at the Laura and Isaac Perlmutter Cancer Center which include annual audits of all patients treated on investigator initiated trials, or by NCI/CTEP or the FDA, BMS, Inc. or its designees may conduct audits of clinical research activities of this trial in accordance with internal Standard Operating Procedures to evaluate compliance with the principles of Good Clinical Practices. BMS, Inc., its designee, or a regulatory authority may wish to conduct an inspection (during the study or after its completion). If an inspection is requested by a regulatory authority, the Investigator will inform BMS, Inc. immediately that this request has been made.

9. ETHICAL ASPECTS

9.1. Ethics and Good Clinical Practice

This study must be carried out in compliance with the protocol and in accordance with the Sponsor-investigator's SOPs. These are designed to ensure adherence to Good Clinical Practice (GCP), as described in the International Conference on Harmonisation (ICH) GCP Guideline (1996) and in accordance with the ethical principles underlying European Union Directive 2001/20/EC and the United States Code of Federal Regulations, Title 21, Part 50 (21CFR50) and Title 21, Part 312 (21CFR312).

The protocol and any amendments and the subject informed consent will receive IRB approval/favorable opinion before initiation of the study. Study personnel involved in conducting this study will be qualified by education, training, and experience to perform their respective tasks. This study will not use the services of study personnel where sanctions have been invoked or where there has been scientific misconduct or fraud (eg, loss of medical license, debarment).

10. STUDY FINANCES

10.1. Funding Source

Funding for conducting the trial will be provided by BMS. The investigational agent will be provided to patients enrolled on this study by Bristol Myers Squibb.

10.2. Subject Stipends or Payments

No patient or subject will receive payments or stipends for participation in this research study. Bristol Myer Squibb may provide coverage for tests and/or procedures that are a part of the research study, if it is not covered by the subject's insurance.

11. PUBLICATION PLAN

Any formal presentation or publication of data collected from this study will be considered for a joint publication by the Investigator(s) and the appropriate personnel of BMS. Authorship will be determined by mutual agreement.

BMS, Inc. must receive copies of any intended public communications of study data or results (eg, manuscripts, posters, abstracts and oral presentations) at least thirty (30) days in advance of their submission. For abstracts, this requirement can be met by providing to BMS, Inc. details about the data and subject matter to be disclosed if a final draft of the abstract is not available 30 days in advance. BMS, Inc. will review the communications for accuracy (thus avoiding potential discrepancies with submissions to health authorities), verify that confidential information is not being inadvertently disclosed, and provide any relevant supplementary information and comments.

12. ADMINISTRATIVE REQUIREMENTS

12.1. Institutional Review Board

Before implementing this study, the protocol, the proposed ICF, and other information provided to subjects must be reviewed and approved by an IRB before study initiation. Any amendments to the protocol which need formal approval, as required by local law or procedure, will be approved by this committee. The IRB will also be notified of all other amendments (ie, administrative changes)

12.2. Protocol Amendments

Any change or addition to this protocol requires a written protocol amendment. Amendments affecting the safety of subjects, the scope of the investigation or the scientific quality of the study, as well as administrative amendments require additional approval by the IRB. All amendments that affect the safety of subjects, the scope of the investigation, or the scientific quality of the study must be approved by BMS and the NCI CTEP prior to implementation. Examples of amendments requiring such approvals are:

1. Increase in drug dosage or duration of exposure of subjects
2. Significant change in the study design (eg addition or deletion of a control group)
3. Increase in the number of invasive procedures to which subjects are exposed
4. Addition or deletion of a test procedure for safety monitoring

These requirements for approval should in no way prevent any immediate action from being taken by the Principal Investigator or by BMS, Inc. in the interests of preserving the safety of all subjects included in the trial. If an immediate change to the protocol is felt to be necessary by the Investigator and is implemented by him/her for safety reasons BMS, Inc. should be notified and the NYULMC IRB should be informed within 10 working days.

14. APPENDICES

Appendix 1: Imaging Methodologies

Contrast enhanced CT or enhanced MRI are the preferred imaging modalities to be used. Chest radiographs performed during the screening phase (and repeated at anytime during the study if clinically indicated) may be used as supportive data, as an accessory to the CT chest scans.

The same imaging techniques used at screening **MUST** be used at all subsequent time points to permit accurate, comparable measurement of lesions. All imaging data are to be collected on film or in digital format.

CT/MRI of the Chest/Abdomen/Pelvis

CT/MRI imaging of the chest, abdomen and pelvis is required at Screening and at each tumor assessment visit as indicated in Table 1, regardless of the location of known prior metastases. In addition, CT/MRI scans must be obtained of anatomic regions not covered by the chest, abdomen and pelvic scans, in subjects where there is clinical suspicion of deep soft tissue metastases indicative of relapse (eg, lesions in the thigh). Such additional CT/MRIs will be required at Screening only when deep soft tissue disease was present and was resected and must be consistently repeated at all subsequent tumor assessment visits.

Brain MRI/CT

Brain scans (MRI or CT) are required at Screening. Brain scans should be conducted during the course of the study as clinically indicated.

Non-radiographic Assessments/Digital Photography

These should be made at the sites and recorded in the source documents. Visible skin lesions indicative of relapse should be measured clinically and documented digitally using standardized photographic images, including a ruler for scale as part of the image.

Image Acquisition Guidelines

Similar methods of tumor assessment and similar techniques must be used to characterize each identified and reported lesion at Screening and during the Induction and Maintenance Phases. Additional assessments may be performed, as clinically indicated, if there is a suspicion of relapse. Imaging-based evaluation is preferred to physical examination. Helical (spiral) CT scans of neck, chest, abdomen and pelvis are preferred. If not available, conventional (non-helical, non-spiral CT) should be used. IV contrast should be used for all CT scans. If i.v. contrast is contraindicated, CT may be performed without contrast. Alternatively, MRI can be used to assess lesions that might be indicative of relapse. Subjects who develop contrast allergy after study enrollment may be followed by MRI for subsequent tumor measurements. Sections should be contiguous, similarly sized and consistent from visit-to-visit. Section thickness must be based on institutional standards (eg, from 5 to 8 mm; 10 mm cuts are not recommended). Chest radiograph, ultrasound, and PET scans are not acceptable methods to routinely assess patients for the presence of disease for the purposes of this study.

Appendix 2: ECOG Performance Status

ECOG PERFORMANCE STATUS	
Grade	ECOG
0	Fully active, able to carry on all pre-disease performance without restriction.
1	Restricted in physically strenuous activity but ambulatory and able to carry out work of a light or sedentary nature, eg, light house work, office work.
2	Ambulatory and capable of all self-care but unable to carry out any work activities. Up and about more than 50% of waking hours.
3	Capable of only limited self-care, confined to bed or chair more than 50% of waking hours.
4	Completely disabled. Cannot carry on any self-care. Totally confined to bed or chair.
5	Dead

Appendix 3: Pre-existing Autoimmune Diseases

Subjects should be carefully questioned regarding their history of acquired or congenital immune deficiencies or autoimmune disease. Subjects with any history of immune deficiencies or autoimmune disease are excluded from participating in the study. Possible exceptions to this exclusion could be subjects with a medical history of such entities as atopic disease or childhood arthralgias where the clinical suspicion of autoimmune disease is low. In addition, transient autoimmune manifestations of an acute infectious disease that resolved upon treatment of the infectious agent are not excluded (eg, acute Lyme arthritis). Please contact the BMS Medical Monitor regarding any uncertainty over autoimmune exclusions.

Diseases that may be autoimmune related include but are not limited to the following:

Acute disseminated encephalomyelitis	Dermatomyositis	Ord's thyroiditis
Addison's disease	Dysautonomia	Pemphigus
Alopecia universalis	Eczema	Pernicious anemia
Ankylosing spondylitis	Epidermolysis bullosa	Polyarteritis nodosa
Antiphospholipid antibody syndrome	acquista	Polyarthritis
Aplastic anemia	Gestational pemphigoid	Polyglandular autoimmune syndrome
Asthma	Giant cell arteritis	Primary biliary cirrhosis
Autoimmune hemolytic anemia	Goodpasture's syndrome	Psoriasis
Autoimmune hepatitis	Graves' disease	Reiter's syndrome
Autoimmune hypoparathyroidism	Guillain-Barré syndrome	Rheumatoid arthritis
Autoimmune hypophysitis	Hashimoto's disease	Sarcoidosis
Autoimmune myocarditis	IgA nephropathy	Scleroderma
Autoimmune oophoritis	Inflammatory bowel disease	Sjögren's syndrome
Autoimmune orchitis	Interstitial cystitis	Stiff-Person syndrome
Autoimmune thrombocytopenic purpura	Kawasaki's disease	Takayasu's arteritis
Behcet's disease	Lambert-Eaton myasthenia syndrome	Ulcerative colitis
Bullous pemphigoid	Lupus erythematosus	Vogt-Kovanagi-Harada disease
Celiac disease	Lyme disease - chronic	Vulvodynia
Chronic fatigue syndrome	Meniere's syndrome	Wegener's granulomatosis
Chronic inflammatory demyelinating polyneuropathy	Mooren's ulcer	
Churg-Strauss syndrome	Morphea	
Crohn's disease	Multiple sclerosis	
	Myasthenia gravis	
	Neuromyotonia	
	Opsoclonus myoclonus syndrome	
	Optic neuritis	

Appendix 4: Description of Use of Blood Samples for Immune Analyses

Detection of Proliferating T cells After NIVOLUMAB + ipilimumab Treatment

Two different but complementary methods (Ki-67 and propidium iodide staining) will be used to detect proliferation of T cells in the peripheral blood of subjects on this trial. Pre-treatment (pheresis), and on weeks 5 and 9 (80 mL sample of blood in green top heparinized tubes on infusion days, prior to infusion) and week 12 follow-up (pheresis) during the trial, PBMC cells will be stained with PI, anti-CD3, anti-CD4, anti-CD8 (T cell markers) and anti-CD56 (NK marker). PI staining will define the proportion of cells in S-phase, and Ki-67 staining with anti-CD3/4/8/56 will define the proliferating compartment. Although it is felt that the proportion of proliferating Ki-67(+) cells and the proportion of cells in S phase will be identical (77), Ki-67 staining will be the “gold” standard to define the proliferating population in case the two parameters are in disagreement. A value of 1.0 % Ki-67 staining will be regarded as minimal evidence for proliferation in subjects based on data from HIV subjects (77). In a recent study in HIV infected subjects, Ki-67 staining was found to correlate closely ($r=0.90$) with an in vivo detection technique for T cell proliferation using deuterated glucose to label the DNA sugar backbone (78). Fresh PBMC will be stained with anti-CD3-PerCP, anti-CD4-APC and anti-CD8-PE (all from Becton-Dickinson). After washing, cells will be lysed at room temperature for 40 minutes, and stained with anti-Ki-67 (MIB-1 from B-D) in PBS with 0.5% NP-40 and 5% FCS at room temperature for 45 minutes. Cells will be washed and fixed with 1% paraformaldehyde and run directly using a FACScan flow cytometer (Beckman-Coulter). All tests will be batched and run simultaneously. The definition of augmented proliferation for the purposes of this trial will be a 20% increase in the absolute proportion of antigen-specific, tetramer positive CD8+ T cells that stain with the Ki-67 marker. We will also assess the phenotype of circulating CD8 and CD4+ T cells in this study using antibodies against markers including HLA-DR, CD25, CD44, CD45 RO/RA, CD62L, CD73, CD95, CD127, FOXP3, PD-1, CTLA-4, BTLA, CD160, Tim3, LAG3, VISTA, 41-BB, OX-40, and ICOS.

Polymorphism Analysis

The four single nucleotide polymorphisms known to be present in CTLA-4 (79-81) and at least six known for PD-1 (82, 83) will be measured by DNA PCR analysis, and a selection of 20% of the total samples will have the results verified by direct DNA sequencing of the relevant areas of DNA. All subjects will be used from the first, and the second trials and the data will be pooled to allow correlations, if any, to be drawn between the presence of a SNP, response, time to progression and development of autoimmunity.

Studies on Regulatory T cells

We propose to study the regulatory activity of CD4⁺CD25⁺ ^{high} cells before and after NIVOLUMAB +ipilimumab treatment. Peripheral blood CD4⁺ T cells will be sorted into CD4⁺CD25⁺ and CD4⁺CD25⁻ populations by flow cytometry. The latter cell subset (responders) will be stimulated with anti-CD3 (10 µg/ml) alone or with anti-CD28 (2µg/ml) and with or without IL-2 (10 IU/ml) in the presence of increasing numbers of sorted CD4⁺CD25⁺ cells. In addition, CD4⁺CD25⁻ will be stimulated with allogeneic mature myeloid dendritic cells (DC), generated from PBMC with GM-CSF and IL-4 and matured with a cytokine cocktail (IL-6, IL-1 beta, TNF-alpha and PGE-2), in the presence or absence of

CD4⁺CD25⁺. The ability of CD4⁺CD25⁺ to suppress the proliferation of CD4⁺CD25⁻ to polyclonal or allogeneic stimulation in a 3 to 5 day proliferation assay using tritiated thymidine incorporation will be determined. We anticipate that CD4⁺CD25⁺ cells will exhibit suppressor activity in vitro as has been previously described and that NIVOLUMAB + ipilimumab treatment will inhibit their suppressive activity in either polyclonal or allogeneic proliferation reaction. We will examine whether loss of suppressor activity of CD4⁺CD25⁺ cells, if found, following NIVOLUMAB + ipilimumab treatment correlates with the development of colitis or other autoimmune side effects. The suppression of allo MLR proliferation by isolated CD4⁺CD25⁺ is an established assay, and well-established in the principal investigator group.

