5.3. Immunology

Evaluations of immunology assessments (below) are summarized in Appendix 4.

- Flow cytometry : Parameters include but may not be limited to the following:
- Blood and peripheral blood mononuclear cell samples will be collected and evaluated by leukapheresis or peripheral blood draw for flow cytometry (T cell, B cell, NK, monocytes, CD3, CD4, CD8, CD4/CD8, CD11b, CD11c, CD14, CD20, CD25, CD33, CD56, CD69, CD71, CD73, CD80, CD127, FOXP3, LAG3, TIGIT, BTLA, Tim3, CTLA-4, PD-1, PD-L1, CD244, OX-40, 41-BB, CD40, CD4/MHC Class II positive cells, and CD8/MHC Class II positive cells), serum cytokines (IL-6, IL-10, TNF- β , ING-gamma, TGF- β , neopterin and sIL-2R), cellular immune function (tetramer and/or ELISpot assays utilizing melanoma and other control antigens).
 - Percent and absolute CD4 and CD8 counts and CD4/CD8 ratio
 - Two color analyses to determine percent and absolute numbers for: CD4/MHC Class II positive cells
 - Two color analyses to determine percent and absolute numbers of: CD8/MHC Class II positive cells

- Serum samples will be collected and cryopreserved to study molecules that may be implicated in regulating anti-melanoma immune responses and/or NIVOLUMAB or ipilimumab activity such as soluble MICA, compounds detected by mass spectroscopy including those associated with wound healing, complement and the acute phase response, chemokines or cytokines, or antibodies to melanoma antigens.
- Cellular Immune Function Assays that may include, but will not be limited to proliferation and/or ELISpot assays utilizing melanoma and other control antigens (Appendix 4).
- Serum samples will be collected and cryopreserved to study molecules that may be identified based on prior analyses of acute phase reactants and may be implicated in regulating anti-melanoma immune responses and/or NIVOLUMAB with ipilimumab activity.

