6.3.4. Immunology Parameters

The data from each of the assays and assessments described in Appendix 4 will be summarized by week of study, using standard descriptive statistical methods – preferably parametric if the distribution of the continuous assay data (possibly after transformation) is compatible with the assumptions of a normal distribution, and non-parametric otherwise. For each immunological marker studied, one of the following 4 transformations will be used: identity (ie, no transformation), square-root, cube root, or log transformation. Choice of the transformation will be made by computing the Anderson-Darling statistic based on the regression model residues using the pooled data. Then the transformation with the lowest Anderson-Darling statistic will be selected as the most normal-like and used in the mixed model analysis.

Scatterplots of the data for the individual subjects, over time, will be constructed to display the patterns; means (or geometric means or medians) with confidence intervals will also be plotted; contingency tables will be used for the categorical assay responses. For baseline and weeks 7 and 13, regression methods (linear or logistic) that accommodate random effects will be used to evaluate the effect of the treatment regimen on the overall levels and on the trends over time – with subject as the random effect and week as the fixed effects. These analyses will be used to evaluate the quantitative effects of the NIVOLUMAB + ipilimumab regimen on immunologic and pharmacodynamic changes due to treatment. While formally proving that the addition of NIVOLUMAB to ipilimumab will increase the probability of clinical benefit is beyond the scope of this trial, the data obtained will be used to test the hypothesis that the magnitude of the proliferating T-cells (as continuous) will increase with NIVOLUMAB added to ipilimumab compared to the prior cohorts of protocol 15651 at Moffitt Cancer Center with NIVOLUMAB alone. Note that the pre and post treatment assays from any given subject that are used in the analysis are always performed on the same plate, thus eliminating a potential confounding factor due to plate-to-plate assay variation.

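### Appendix 4 takes interim proliferation samples from a different cell source than baseline, so interim contrasts and a categorical week test mix source with time, and the source at the modelled weeks is not stated

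*Combined protocol and SAP*

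**What the plan says.** Appendix 4, on detecting proliferating T cells, ties the cell source to the visit. It gives the baseline and interim samples as "Pre-treatment (pheresis), and on weeks 5 and 9 (80 mL sample of blood in green top heparinized tubes on infusion days". For the last sample it returns to the first method: "and week 12 follow-up (pheresis) during the trial". So the two end samples are pheresis products and the two middle samples are heparinized blood.

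Section 5.3 points to Appendix 4 but then describes the flow cytometry samples as "collected and evaluated by leukapheresis or peripheral blood draw for flow cytometry", without tying either method to a visit. The synopsis does the same.

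Section 6.3.4 specifies the analysis: "For baseline and weeks 7 and 13, regression methods (linear or logistic) that accommodate random effects will be used" to assess the effect of the regimen on levels and on trends over time, "with subject as the random effect and week as the fixed effects". It does not say whether week is a category or a number. The one technical factor it addresses is the plate: pre- and post-treatment assays from a subject "are always performed on the same plate, thus eliminating a potential confounding factor due to plate-to-plate assay variation".

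The secondary immune objective (Section 1.6) and the definition of augmented proliferation (Section 6.3.4.1) are both set at Week 12. Section 5.6.3 reports the proliferation response rate at baseline and weeks 7 and 13.

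**The concern.** Where collection method changes with visit, a difference between pheresis cells and tube-blood cells looks the same as a change over time. The model has no term for it, and with week as a category no term added later could separate the two. An early on-treatment change, which is what an interim sample is meant to show, could then be partly or wholly a difference in how the cells were obtained.

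The plan accepts the principle for plates, holding them constant within a subject so that they cannot confound the pre/post comparison. Cell source is a technical factor in the same comparison and is neither held constant nor recorded.

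The schedules also disagree. Appendix 4 samples at weeks 5, 9 and 12 and calls weeks 5 and 9 infusion days, Table 1 places cycle 1 infusions at weeks 1, 4, 7 and 10, and Sections 5.6.3 and 6.3.4 analyse weeks 7 and 13. The source of the samples that actually enter the model therefore cannot be read from the documents.

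**Working it through.** The plan states no power or effect size for the time trend, so there is no figure of its own to reproduce. The check has three parts.

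**Inputs.** From the documents: the source by week (Appendix 4), the model weeks and terms (Section 6.3.4), two-sided 0.05 (Section 6.3), and 20 subjects (Section 4.3). Assumed: a constant source shift δ between tube and pheresis cells, and the within-subject correlation r. Neither is given.

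**1. Can source be separated from week?** Take weeks 0, 5, 9, 12 with source indicator s = (0, 1, 1, 0), where 1 is tube blood.
- Categorical week plus source: 5 columns, rank 4. Source is fully aliased.
- Linear week plus source: 3 columns, rank 3. Source is separable.

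**2. How much of δ enters each estimate?** A contrast with baseline carries s(week) − s(0). The least-squares slope carries Σ(w − w̄)s / Σ(w − w̄)², multiplied by the span.
- *Appendix 4 weeks.* Week 5: 1.0 δ. Week 9: 1.0 δ. Week 12: 0. Slope: w̄ = 6.5, numerator −1.5 + 2.5 = 1.0, denominator 81, so 0.0123 δ per week, or 0.15 δ over 12 weeks.
- *Section 6.3.4 weeks (0, 7, 13), if week 7 is tube and week 13 pheresis.* w̄ = 6.667, denominator 84.67, numerator 0.333. Slope bias 0.05 δ over 13 weeks; week 13 contrast 0; week 7 contrast 1.0 δ.
- *The same weeks, if both are tube.* Numerator 0.333 + 6.333 = 6.667. Slope bias 1.02 δ over 13 weeks; week 13 contrast 1.0 δ.

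**3. False-positive rates with no true time effect.** For a paired test of one interim visit against baseline, the SD of the difference is √(2(1 − r)) SD. The noncentrality is δ√20 / √(2(1 − r)), on 19 df with critical value 2.093. Here δ is in between-subject (total) SD units.

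| δ (SD) | r = 0.5: noncentrality | r = 0.5: rate | r = 0.7: noncentrality | r = 0.7: rate |
|---|---|---|---|---|
| 0.1 | 0.447 | 0.071 | 0.577 | 0.085 |
| 0.25 | 1.118 | 0.186 | 1.443 | 0.278 |
| 0.5 | 2.236 | 0.565 | 2.887 | 0.782 |
| 0.75 | 3.354 | 0.889 | 4.330 | 0.984 |

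For tests within the random-intercept model, with δ in within-subject (residual) SD units of 0.25 / 0.5 / 1.0, the rates are as follows. The overall week test is from the noncentral F distribution, the rest from 20,000 simulations.

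| Test | Rate |
|---|---|
| Weeks 0/5/9/12, overall categorical week | 0.13 / 0.41 / 0.97 |
| Weeks 0/5/9/12, week 5 versus baseline | 0.12 / 0.34 / 0.87 |
| Weeks 0/5/9/12, week 12 versus baseline | 0.05 / 0.05 / 0.05 |
| Weeks 0/5/9/12, linear slope | 0.05 / 0.05 / 0.04 |
| Weeks 0/7/13, both tube, linear slope | 0.12 / 0.35 / 0.87 |

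The two tables use different SD units and should not be compared row by row.

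**The case against.** A reader might infer that the whole mixed-model time trend is unreadable. The documents do not support that, for four reasons, and all four stand.

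- The visit that carries the objective and the response definition is Week 12. Under Appendix 4 it is compared pheresis to pheresis, with no bias.
- The tube samples lie between two pheresis samples, so a linear slope over the Appendix 4 weeks takes up only about 0.15 of the shift. Its false-positive rate stays at or below nominal. Source is also separable from linear week.
- The model is specified for weeks 7 and 13, not the Appendix 4 weeks. Whether it is affected depends on sources that are not stated.
- Nothing in the documents shows that pheresis and tube cells differ in Ki-67 proportion. The shift is assumed, and at zero shift there is no problem.

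It can also be said that Section 5.3 refers to Appendix 4, so its either-source wording may only mean that some visits use one method and some the other. That is a fair reading for the proliferation assay. It does not settle weeks 7 and 13, which Appendix 4 does not mention.

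Finally, the immune analyses are exploratory, and no stated dosing, stopping or sample-size rule depends on them. That limits the seriousness of the point. It does not remove the reason to act, because aliasing of categorical week with source cannot be undone once samples are taken.

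**Conclusion.** The point holds in a limited form. On the Appendix 4 schedule, interim-versus-baseline contrasts carry the full source shift, and a categorical week test picks it up as well. Week 12 versus baseline does not, and a linear slope hardly does. For the weeks that Section 6.3.4 models, exposure cannot be determined. It runs from 0.05 δ in the slope and none in the final contrast (week 7 tube, week 13 pheresis) to essentially all of δ in both (both tube against a pheresis baseline).

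The false-positive range of 7% to 89% applies only to a paired interim-versus-baseline test with 20 subjects, correlation 0.5 and assumed shifts of 0.1 to 0.75 SD. It is not a statement about the Week 12 result. This is a cheap improvement to a secondary, exploratory analysis. The primary safety objective is untouched.

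**What to change.** - Reconcile the sampling and analysis weeks across Section 5.6.3, Section 6.3.4, Table 1 and Appendix 4, and state the cell source for each modelled week.
- In Sections 5.3 and 6.3.4, require the same source for both samples of any tested contrast: pheresis to pheresis for baseline versus Week 12.
- State in Section 6.3.4 whether week is categorical or linear.
- Record the source of every sample in the dataset.
- Report mixed-source interim results descriptively, or test them only against a blood-draw baseline if one is kept. Table 1 lists Day 1 research samples but not their source, so it does not show that such a baseline exists.

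There is no need to confine testing to a single contrast; any like-for-like contrast can stay. The cost is protocol and SAP wording and one recorded field. The downside is that formal interim tests are lost where no blood-draw baseline is available. The source rule is needed before sampling, because it cannot be applied to samples already taken.
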